10.1.1 Subject and Investigator In-clinic Assessment

Subjects will be trained extensively in accurate self-assessment of their glabellar line severity by the investigator at the baseline visit, as outlined in FWS completion manuals 'Glabellar Line Scale – Subject: Completion Manual' and 'Glabellar Line Scale - Subject: Completion Manual for Investigator'. Investigators will complete training before trial initiation and will receive training certification. Investigators will also have an FWS completion manual: 'Glabellar Line Scale – Investigator: Completion Manual'. Subject FWS assessment must be performed independently of the investigator and ideally before the investigator FWS assessment, to rule out any influence or bias from the investigator. The date and time of assessment will be recorded for each visit in the double blind cycle and for the week 4 visits during the open label cycles.

Subjects and investigators will assess the severity of the subject's glabellar lines at maximum frown and at rest using the FWS instrument (Section20.1), i.e. the GLS-S (for subjects) and the GLS-I (for investigators).

In the first treatment cycle, the severity of the subjects' glabellar lines will be evaluated by the subject and the investigator at baseline and at study visits 1, 2, 4, 8, 12 weeks and at 4 weekly intervals thereafter (week 16, week 20, etc.) until the subject qualifies for re-treatment with glabellar line severity returning to a score of 2 or 3 on the FWS. The same investigator must assess the subjects at baseline and at the visits at weeks 1, 2 and 4 in the first treatment cycle,

although every effort shall be made to have the same investigator assess subjects at all time points.

The primary efficacy endpoint will be a composite endpoint of the investigators' and the subjects' assessments of line severity at maximum frown in comparison with placebo at week 4. A subject will be considered a responder if they have a FWS score of 0 or 1 and an improvement ≥ 2 points in FWS score (at maximum frown) at the week 4 visit (of the first treatment cycle) relative to baseline, based on both the investigator's and the subject's inclinic assessments. Responder rates at other time points in the first treatment cycle will be evaluated as secondary endpoints.

In the open label extension phase, the percentage of responders (FWS score of 0 or 1 and an improvement \geq 2 points in FWS score at maximum frown) at week 4 after re-treatment relative to the rating at the preceding end of cycle visit will be determined as a secondary efficacy endpoint.

10.1.2 Photo-evaluator Assessment

Photography will be performed by specifically trained personnel in accordance with the relevant imaging manual. Photographs of subjects at maximum frown and at rest will be taken in the first treatment cycle at the following visits: baseline before the first treatment, study visits 2 and 4 weeks after the first treatment and at the Evaluation for Re-treatment visits, i.e. week 12 after baseline and 4 weekly thereafter until the subject qualifies for re-treatment. Selected photographs will subsequently be assessed by independent blinded raters. Although a photograph will be taken at each evaluation for the re-treatment visit, only the photograph of the visit preceding the re-treatment visit will be reviewed by the independent raters (in addition to the photographs at baseline, week 2 and week 4) and the data will be included in the analysis of additional secondary efficacy endpoints.

10.2 Psychological Impact

The psychological impact of glabellar lines and concerns relating to glabellar lines will be measured using the modified Skindex-16 (GL-QoL) Scale⁴³ (Section 20.3) and the FACE-Q Appraisal of Lines Between Eyebrows scale and Age Appraisal VAS ⁴⁴ (Section 20.4), respectively, at screening, 4weeks after each treatment and the end of each treatment cycle.

10.3 Subject Satisfaction with Treatment

Treatment satisfaction will be measured using the FACE-Q Satisfaction with Outcome Scale⁴⁵ (Section20.6) at 4 weeks after each treatment administration and at the end of each treatment cycle.

11. ASSESSMENT OF SAFETY

11.1 Adverse Events

An AE is defined as any untoward medical occurrence in a subject administered an IMP that does not necessarily have a causal relationship with the treatment. An AE can therefore be any unfavorable and unintended sign (including an abnormal laboratory finding), symptom, or disease temporally associated with the use of an IMP, whether or not related to the IMP. AEs will be recorded from signing the ICF until the End of Study visit. SAEs and AESIs are subgroups of AEs as defined below. Any remark for AEs in general also applies to AESIs and SAEs.

Any pre-existing conditions or signs and/or symptoms present in a subject prior to the start of the study (i.e. before informed consent) should be recorded as Medical History; however any increase in severity, frequency or duration of a pre-existing disease during the course of the study will be recorded as an AE. Clinically significant test results at screening will be recorded as Medical History. Any untoward medical occurrence in a subject between ICF and first dose will be recorded as a Pre-treatment Event on the Medical History page. Any untoward medical occurrence in a subject after first dose until End of Study visit will be recorded as an AE. All AEs, AESIs, and SAEs must be recorded, irrespective of whether they are considered study drug related.

The investigator may contact the Sponsor's Medical Expert if additional information is needed for the assessment of AEs.

11.1.1 Clinical Laboratory Abnormalities and Other Abnormal Assessments as AEs, AESIs, and SAEs

Newly detected abnormal clinical laboratory findings (e.g. clinical chemistry, hematology) or other abnormal assessments (e.g. ECGs, physical examination, vital signs) that are judged by the investigator as clinically significant must be recorded as AEs, AESIs, or SAEs. Clinically significant abnormal clinical laboratory findings or other abnormal assessments present at the Screening visit will be documented as Medical History. If there is worsening during the study this will be documented as an AE, AESI, or SAE.

The investigator will exercise medical and scientific judgment in deciding whether an abnormal clinical laboratory finding or other abnormal assessment is clinically significant.

11.2 Adverse Events of Special Interest

A specific concern in treatment with botulinum toxin products is the potential for local and distant spread of toxin effect, a unique set of safety concerns related to use of botulinum toxin drug products (draft guidance for industry *Upper Facial Lines: Developing Botulinum Toxin Drug Products*). Therefore, subjects will be instructed and educated on possible warning signs and precautions and on rare AESIs through the Subject Information Sheet (SIS). Safety data related to this specific potential effect should be obtained through directed query at each study visit and if an AESI as below is reported a targeted physical examination should be

conducted to evaluate for signs and symptoms of local and distant spread of toxin effect. AESI assessment and documentation is mandatory based upon the event term. An AESI must also be reported even if e.g. duration of the event is to considered unusual for an AESI or if the event is considered as being not related to the study drug. Adverse events of special interest potentially suggestive of distant spread of toxin, include:

accommodation disorder areflexia aspiration blurred vision botulism bradycardia bulbar palsy constipation cranial nerve palsies cranial nerve paralysis diaphragmatic paralysis diplopia dry mouth dysarthria dysphagia	dyspnea extraocular muscle paresis eyelid function disorder eyelid ptosis facial palsy facial paresis fourth cranial nerve paresis hemiparesis hypoglossal nerve paresis hyporeflexia hypotonia monoparesis muscular weakness paralysis paralytic ileus	Paresis peripheral nerve palsy peripheral paralysis pelvic floor muscle weakness pneumonia aspiration pupillary reflex impaired quadriparesis respiratory arrest respiratory failure speech disorder third cranial nerve paresis trigeminal nerve paresis urinary retention vocal cord paralysis
dysphagia	paralytic ileus	vocal cord paralysis
dysphonia	paraparesis	vocal cord paresis

The first AESI questioning will be undertaken (in accordance with the AESI Manual) prior to the first injection, in order to obtain a full baseline status of any concomitant diseases. If an AESI is reported, a targeted physical examination must be conducted. If reported during a telephone contact, subjects must come to the site for further assessment as soon as possible.

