4.6.2 Possible Risks/Inconveniences for the Subject

Botulinum toxin drug products present a unique set of safety concerns related to the potential for local and distant spread of toxin effect. Therefore, an active evaluation of subjects for signs and symptoms of local and distant spread of toxin effect will be performed throughout the study at each study visit. Subjects will be warned about signs of the spread of toxin effects including asthenia, generalized muscle weakness, diplopia, ptosis, dysphagia, dysphonia, dysarthria, urinary incontinence, breathing difficulties and possible adverse events of special interest (AESIs, please see Section 11.1). Respiratory, speech or swallowing difficulties can also result, which could be life threatening, however no definitive SAE reports of distant spread of toxin effect associated with cosmetic or dermatologic use of botulinum toxin at the labeled dose of 20 U (for glabellar lines) or 100 U (for severe primary axillary hyperhidrosis) have been reported to date. Baseline physical examinations will also be conducted to rule out pre-existing neurological or muscular deficiencies. In addition, key safety measures such as vital signs and pregnancy tests (where appropriate) will be conducted at suitable intervals to ensure no participating subjects are pregnant.

As is the case with all injected products, injection site reactions such as pain, tenderness, redness, induration and/or swelling may occur after administration. In addition, a number of other symptoms have been experienced by single subjects including pruritus, hypertonia, ptosis, headache, diplopia, edema and blurred vision. The most frequently observed injection site reactions were injection site pain and swelling. The vast majority of AEs were rated as mild.

In addition, as with any IMP, there may be unforeseeable risks associated with the use of BoNT/A-DP or placebo control. As a side effect of drawing blood, pain, hematoma, and in very rare cases an infection at the venipuncture site may occur.

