11.6.1 Reporting Serious Adverse Events and Adverse Events of Special Interest

All SAEs and AESIs for all subjects occurring from the time of informed consent until the End of Study visit must be reported to CROMA Pharma GmbH or their representative within 24 hours of the knowledge of the occurrence. If considered at least possibly related to study treatment, SAEs observed after the End of Study visit must also be reported.

Paper SAE/AESI forms should be completed at the site and faxed to the Medical & Safety Services Department Clinical Research within 24 hrs of awareness of the event.

The preferred way of submitting the safety reports is via the above email address. Fax numbers have been provided as back up.

If the report is sent via email then the completed and signed SAE/AESI or Pregnancy report form must be attached to the email. A notification email of the event describing it in the email text is not sufficient.

There may be situations when an SAE/AESI has occurred and the investigator has minimal information to include in the initial SAE/AESI report to CROMA Pharma GmbH, or their representative. However, it is very important that the investigator always makes an assessment of causality for every event prior to transmission of the SAE/AESI report form. Minimum criteria are identifiable subject (number), a suspect product (i.e. IMP or concomitant medication), an identifiable reporting source (investigator/study-site identification) and an event or outcome that can be identified as serious or as an AESI. The investigator may change his/her opinion of causality in the light of follow-up information, amending the SAE/AESI report form accordingly. The causality assessment is one of the criteria used when determining regulatory reporting requirements for SAEs.

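### The AESI term list in Protocol 11.2 leaves out asthenia and urinary incontinence, which Protocol 4.6.2 names as signs of toxin spread, so non-serious cases may not be handled or tabulated as AESIs unless the AESI Manual adds them

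*Protocol*

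**What the plan says.** **Signs of spread.** In Protocol 4.6.2, the warning given to subjects covers "signs of the spread of toxin effects including asthenia, generalized muscle weakness, diplopia, ptosis, dysphagia, dysphonia, dysarthria, urinary incontinence, breathing difficulties". That is nine signs, and possible AESIs are mentioned after them.

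**AESI list.** Protocol 11.2 opens the list with "Adverse events of special interest potentially suggestive of distant spread of toxin, include" and prints 47 terms in three columns.

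**What makes an event an AESI.** The same section states: "AESI assessment and documentation is mandatory based upon the event term". It ties the targeted physical examination to a report of one of the AESIs listed below that sentence.

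**What AESI status triggers.**
- 24-hour reporting. Protocol 11.6.1: "All SAEs and AESIs for all subjects occurring from the time of informed consent until the End of Study visit must be reported" within 24 hours of the site learning of the event.
- A call-in to the site when the event is reported by telephone (Protocol 2.1 notes, Table 9-1 note 7, 9.3.1 and 11.2).
- Separate AESI tables (Protocol 12.4.2; SAP 8.7.2 and 8.9).

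The SAP relies on AESI status throughout but prints no list of AESI terms.

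**The concern.** Spread of toxin effect is the product-specific safety concern that the protocol names, and the AESI tables are the dedicated summary of it. If classification goes by event term, two events that the protocol itself calls signs of spread have no stated route into that summary. A site that applies 11.2 literally to new, non-serious urinary incontinence after a re-treatment would have grounds to record an ordinary AE and stop there. This matters most at weeks 2 and 8 of each open-label cycle. Those contacts are by telephone, and AESI status is the only stated mandatory reason to bring the subject in.

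**Working it through.** No figure in the plan bears on this point. The check sets the two lists side by side and then follows the rules that depend on AESI status.

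**Step 1. Is the list complete as printed?** The columns hold 16, 16 and 15 terms: 16 + 16 + 15 = 47. The order is close to alphabetical. Where asthenia would fall, the text reads "accommodation disorder areflexia aspiration blurred vision botulism". Where urinary incontinence would fall, it reads "trigeminal nerve paresis urinary retention vocal cord paralysis". Neither place shows a gap, so loss in text extraction is unlikely.

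**Step 2. Match the nine signs in 4.6.2 to the terms in 11.2.**

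| Sign in 4.6.2 | Term in 11.2 |
|---|---|
| diplopia | diplopia |
| dysphagia | dysphagia |
| dysphonia | dysphonia |
| dysarthria | dysarthria |
| generalized muscle weakness | muscular weakness |
| ptosis | eyelid ptosis |
| breathing difficulties | dyspnea |
| asthenia | none |
| urinary incontinence | none |

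Matched: 7 of 9. Unmatched: 2 of 9 = 22%.

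**Step 3. Does a neighbouring term cover the two?** For asthenia the nearest is in the run "hypotonia monoparesis muscular weakness paralysis paralytic ileus". But 4.6.2 lists asthenia and generalized muscle weakness as two separate signs, so the protocol does not treat them as one. For urinary incontinence the nearest are urinary retention and pelvic floor muscle weakness, which are different event terms. Under a term-based rule, a near neighbour does not qualify.

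**Step 4. What happens to a case recorded under either term, on the protocol and SAP text alone?**

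| Handling | Non-serious | Serious |
|---|---|---|
| Recorded as an AE | yes | yes |
| TEAE tables by SOC and PT | yes | yes |
| 24-hour report | no stated route | yes, as an SAE |
| Targeted examination under 11.2 | no stated route | no stated route |
| Call-in after a telephone report | no stated route | no stated route |
| AESI tables | no stated route | no stated route |

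**Step 5. Can the number of affected subjects be estimated?** No. The documents give no incidence for either term. The BLESS summaries in Protocol 4.4.2.1 and 4.4.2.2 do not name either one, but BLESS I groups its remaining related events as affecting no more than one subject each, so this does not show that there were none.

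**The case against.** The best case on the other side has five parts.

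- **The list may not be closed.** It is introduced by the word *include*, and the AESI questioning follows an AESI Manual that is not among the documents. The Protocol 2.1 notes require a focused examination for any symptoms related to AESIs as that Manual details them. This stands, and it is why the conclusion is conditional. But if the list is open, 11.2 gives sites and programmers no criterion for adding terms, so that reading needs correcting too.
- **Section 4.6.2 is a warning to subjects, not a definition of AESIs.** True, and the two lists need not be identical. Still, 11.2 describes its terms as possible indicators of distant spread, and 4.6.2 calls these two events signs of spread. The protocol gives no reason for leaving them out.
- **Other safeguards exist.** Section 4.6.2 promises active evaluation for spread at each study visit. Full examinations at week 1, week 4 and end of cycle or study include assessment for muscle weakness (Protocol 2.1 and 11.11). Investigators must evaluate any AE, and an unscheduled visit is possible at any time. This stands and limits the consequence, more for weakness than for continence, which the description of the examination does not mention.
- **Asthenia is non-specific.** True, but so are constipation, dry mouth and bradycardia, which are listed.
- **Adding cases afterwards mixes ascertainment.** Earlier cases would have had no AESI form or targeted examination. This stands, and the fix has to mark them.

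A reader might infer that these events go undetected, or that the AESI count is understated by some percentage. The documents support neither. The events are recorded and tabulated as TEAEs, and serious ones are reported within 24 hours. A percentage would need an assumed incidence in this trial of 353 planned subjects, set against AESI counts from BLESS trials of other sizes (708 and 213 subjects).

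**Conclusion.** The mismatch is real and can be read directly from the protocol: two of the nine signs of spread named in 4.6.2 have no term in the 11.2 list, and the SAP does not repair this. The consequence is narrower than the mismatch may suggest. It concerns non-serious cases for 24-hour reporting, and otherwise the targeted examination, the call-in and the AESI tables. It rests on one assumption that cannot be checked here, namely that the AESI Manual does not add the two terms. If the Manual does add them, what remains is an inconsistency between it and Protocol 11.2. The number of subjects affected cannot be estimated. The point bears on safety ascertainment only; no sample size, power, alpha or efficacy result changes. It should be corrected because the correction is cheap and concerns the trial's own named safety issue.

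**What to change.** 1. **Protocol and AESI Manual.** Reconcile 4.6.2, 11.2 and the Manual so that every sign of spread the protocol names is covered by the AESI term list. State in 11.2 whether the list is exhaustive and, if not, which document governs additions.
2. **SAP 8.7.2 and 8.9.** Add a line that tabulates coded TEAEs with the preferred terms asthenia and urinary incontinence together with the AESIs. Mark any recorded before the list was corrected, because they had no AESI form or targeted examination, so that the two kinds of ascertainment can be told apart.

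**Cost.** A short list change, a matching SAP line, and some additional 24-hour reports and examinations. The SAP step uses events already collected and coded. The downside is that asthenia is non-specific and will bring some unrelated events into the AESI tables in both arms.

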11.3 Serious Adverse Events

An SAE is defined as an untoward medical occurrence that at any dose meets one or more of the following criteria:

- Results in death.
- Is life threatening defined as an event in which the subject was, in the judgment of the investigator, at risk of death at the time of the event; it does not refer to an event that hypothetically might have caused death had it been more severe.
- Requires subject hospitalization or results in prolongation of existing hospitalization.
- Results in persistent or significant disability/incapacity.
- Is a congenital anomaly/birth defect.
- Is an important medical event.

Note: Medical or scientific judgment should be exercised in deciding whether reporting is appropriate in other situations, such as important medical events that may not be immediately life threatening or result in death or require hospitalization but may jeopardize the subject or may require medical or surgical intervention to prevent one of the other outcomes listed in the definitions above. Examples of such events are: invasive or malignant cancers, intensive treatment in an emergency room or at home for allergic bronchospasm, blood dyscrasias, or convulsions that do not result in hospitalization, or development of drug dependence or drug abuse. Hospitalization is defined as at least 1 overnight stay. Pre-planned hospitalizations (known already prior to signing the ICF) will not be considered an SAE, unless any of above criteria are fulfilled over the course of the hospitalization due to unplanned complications.

11.4 Treatment-Emergent Adverse Events (TEAEs)

A TEAE is defined as any event not present prior to the initiation of the treatment, or any event already present that worsens in terms of severity, duration, or frequency following exposure to the treatment.

11.5 Evaluation of AEs, AESIs, SAEs, TEAEs

11.5.1 Assessment of Causality

The investigator is obliged to assess the relationship between the IMP as well as study procedure and the occurrence of each AE/AESI/SAE. This relationship will be classed as not related, unlikely, possibly, probably or definitely related as follows:

- Not related (both circumstances must be met):
 - ➤ Is due to underlying or concurrent illness, complications, concurrent treatments, or effects of concurrent drugs.
 - ➤ Is not associated with the IMP or study procedure (i.e. does not follow a reasonable temporal relationship to the administration of IMP or has a much more likely alternative etiology).
- Unlikely related (either one or both circumstances are met):
 - > Has little or no temporal relationship to the IMP or study procedure.
 - A more likely alternative etiology exists.
- Possibly related (both circumstances must be met):
 - > Follows a reasonable temporal relationship to the administration of IMP.
 - An alternative etiology is equally or less likely compared to the potential relationship to the IMP or study procedure.
- Probably related (both circumstances must be met):

- Follows a reasonable temporal relationship to the administration of IMP, which may include but is not limited to the following:
 - o Reappearance of a similar reaction upon re-administration (positive re-challenge).
 - o Positive results in a drug sensitivity test (skin test, etc.).
 - oToxic level of the IMP as evidenced by measurement of the IMP concentrations in the blood or other bodily fluid.
- Another etiology is unlikely or significantly less likely
- Definitely related:
 - ➤ Has clear and undoubted relationship to the administration of IMP.

The investigator will use his/her clinical judgment to determine the relationship. Alternative causes, such as natural history of the underlying diseases, concomitant therapy, other risk factors, and the temporal relationship of the event to IMP administration will be considered and investigated. The investigator will also consult the IB in the determination of his/her assessment.

For the purpose of expedited regulatory reporting, events assessed as possibly, probably, or definitely related to IMP or study procedure will be considered as drug related.

